2.2.2. SAFETY ASSESSMENTS

Safety and tolerability will be assessed by evaluating the following:

Document: T:\Shire\Teduglutide\XXA39799\Biostatistics\Documentation\SAP\SHP633-302 SAP Final

1.0_17Apr2019.docx

Version Number: Final 1.0
Version Date: 17Apr2019

Template No: CS TP BS016 Revision 4

Effective Date: 01Apr2016

Author:

Reference: CS_WI_BS005

- Adverse events, including those pertaining to GI symptoms.
- Physical examinations, including body weight, height (or length), head circumference (up to 36 months of age), and trends on growth charts
- Vital signs, including temperature, heart rate, blood pressure
- Electrocardiograms (ECGs)
- Laboratory safety data (ie, biochemistry, hematology, coagulation, urinalysis)
- Urine output
- Fecal output (by volume or number of bowel movements per day)
- Antibodies to teduglutide
- For children 1 to 15 years of age: GI-specific testing including colonoscopy or sigmoidoscopy, abdominal ultrasound, fecal occult blood testing, upper GI series with small bowel followthrough (UGI/SBFT)
- For infants 4 to <12 months corrected gestational age: UGI/SBFT

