6. STATISTICAL/ANALYTICAL ISSUES

6.1. GENERAL METHODOLOGY

All statistical procedures will be completed using SAS version 9.4 or later.

Document: T:\Shire\Teduglutide\XXA39799\Biostatistics\Documentation\SAP\SHP633-302 SAP Final

1.0 17Apr2019.docx

Author: Version Number: Final 1.0 Version Date: 17Apr2019

Template No: CS_TP_BS016 Revision 4 Reference: CS_WI_BS005

Effective Date: 01Apr2016

Copyright © IQVIA. All rights reserved.

Due to the limited size of the study population descriptive statistics will be used with a goal of summarizing the sample which discourages the use of inferential statistics. Accordingly, no claims of significance will be made for any of the data.

Continuous variables, including those assessed on a discrete scale, will be summarized using descriptive statistics including number of subjects, mean, median, standard deviation, maximum, and minimum. Standard errors (SE) will be displayed for the efficacy tables, and body weight, height (or length), BMI, head circumference and weight for length. For categorical variables, descriptive statistical summaries will include number of subjects and percentages.

For summary purposes, the baseline value will be defined as the last available pre-dose value. Scheduled visits will be summarized as provided in the electronic case report forms (eCRFs). An End of Treatment (EOT) time point, defined as the last determination of endpoint or last available measurement after the date of first dose during the 24-week treatment period will be analyzed in addition to the scheduled visits. Similarly, an End of Study (EOS) time point will be defined as the last determination of endpoint or last available measurement after the EOT during the 4-week follow-up period. Unscheduled measurements will not be included in by-visit summaries, but can contribute to the EOT/EOS value where applicable.

Study Day will be calculated as follows:

- If the date of the evaluation is on or after the first day of study medication then: Study Day = (date of the evaluation – first day of study medication) + 1.
- If the date of the evaluation is prior to the first day of study medication then: Study Day = (date of the evaluation – first day of study medication).

Datasets and listings will include data collected at unscheduled visits. Data collected at unscheduled visits will not be included in summaries by timepoint or visit unless specified otherwise.

Data will be analyzed and presented by subject cohorts:

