13.9. FECAL AND URINE OUTPUT

Output diary data is recorded over a 48 hour period of PN/IV and EN stability before every scheduled site visit and within 1 week of implementing any PN/IV prescription adjustment. For

Document: T:\Shire\Teduglutide\XXA39799\Biostatistics\Documentation\SAP\SHP633-302 SAP Final

1.0_17Apr2019.docx

Version Number: Final 1.0 Version Date: 17Apr2019

Reference: CS WI BS005

Template No: CS TP BS016 Revision 4

Effective Date: 01Apr2016

Author:

Copyright © IQVIA. All rights reserved.

the analysis, the latest 48-hour period of output diary data entered prior to each visit will be used (The 48-hour period does not need to be within 48 hours of the visit). Any additional output diary data collected out of this 48-hour window will only be presented in the listings.

The average daily urine output (mL/kg/day) at the scheduled site visit will be calculated as follows:

(Total urine output over 48 hours / 2) / most recent body weight (kg) prior to or on the scheduled visit

where total urine output is calculated as the sum of the urine output in mL and the urine-only diaper weights in g (1g = 1mL) for the subject collected on the output diary form of eCRF over 48 hours. Values will not be calculated if the urine output is not available at the visit.

The average daily fecal output will be summarized separately by the number of stools per day, the typical stool form score using Bristol Stool Form Scale, the total daily stool/mixed stool diaper weight (g/kg/day) and the total ostomy output per day (mL/kg/day). The number of stools per day and the average typical stool form score will be calculated as (sum of the daily data in a 48-hour period / 2). The body weight will be used to calculate the daily stool/mixed stool diaper weight (g/kg/day) and the total ostomy output per day (mL/kg/day) using a formula analogous to that used to calculate the average daily urine output.

The change and the percent change in average daily output for urine and fecal from baseline to each scheduled visit, as well as at EOT, will be presented using descriptive statistics defined in Section 6.1.

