5 STUDY DESIGN

Protocol SHP633-302 was a 24-week safety, efficacy, pharmacodynamic, and PK study of teduglutide in Japanese pediatric subjects, aged 4 months through 15 years, with short bowel syndrome (SBS) who are dependent on parenteral support. Planned enrollment is a minimum of 5 subjects aged 1 through 15 years and a minimum of 2 subjects of 4 to <12 months corrected for gestational age.

A schematic representation of the study design is presented in Figure 1.

Figure 1. Study Design (SHP633-302)

EOS=end of study; EOT=end of treatment

During the treatment period, a SC dose of 0.05 mg/kg/day of teduglutide was administered once daily to the subjects for 24 weeks. The dose calculation was based on body weight measured at the baseline visit (visit 2) and may be adjusted at Week 12 (visit 14).

Subjects participated in a minimum 2-week screening period from the time of the screening visit to the baseline visit, followed by 24 weeks of treatment. Attempts were made to limit the screening period to 4 weeks. The EOS visit was scheduled at Week 28, 4 weeks after the EOT visit (Week 24).

Following reconstitution, teduglutide was administered by SC injection once daily into 1 of the 4 quadrants of the abdomen (in subjects without a stoma) or into either the thigh or arm. For subjects with a stoma, the quadrant of the abdomen containing the stoma was not used. Each day, the injection site was to be rotated. The site of administration (arm, thigh, or abdomen) of the first teduglutide dose was specified and recorded in the eCRF.

Blood samples for teduglutide concentrations were collected at the baseline and at the Week 4 visits as presented in Table 1.

Table 1. Blood Sample Collection Schedule for Pharmacokinetic Testing

Study week	Baseline		Week 4			
Visit Number		2			6	
Hour	0^a	1	6	0^{a}	2	4

^a Prior to investigational product administration

Some deviations from the above timepoints may have occurred. The investigator or designee kept deviations to a minimum and guided by the following collection windows:

- 0-h (predose) draw: any time prior to the daily dose, on the day of dosing, but at least 14 h after the previous dose (at the week 4 draw).
- 1-h postdose draw: ±10 min
- 2-h postdose draw: ± 10 min
- 4-h postdose draw: ±30 min
- 6-h postdose draw: ±30 min

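### Section 13.9 applies percent change from baseline to the Bristol stool form score, an ordinal code with no true zero, so the result depends on how the categories are numbered

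*SAP*

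**What the plan says.** SAP Section 13.9 (Fecal and Urine Output) splits average daily fecal output into four separately summarized measures: number of stools per day, "the typical stool form score using Bristol Stool Form Scale", stool/mixed stool diaper weight per kg, and ostomy output per kg. The daily form score is averaged over the 48-hour diary window by summing the daily values and dividing by 2.

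The last paragraph of the section then orders "The change and the percent change in average daily output for urine and fecal from baseline" to each scheduled visit and to EOT, using the statistics of Section 6.1. Those statistics include the mean and the median, and Section 6.1 extends them to variables recorded on a discrete scale. Neither section exempts the stool form score from percent change.

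Three further statements set the context:

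- Section 2.2.2 lists the safety assessment as "Fecal output (by volume or number of bowel movements per day"; stool form is not named there.
- Section 6.1 says "Accordingly, no claims of significance will be made for any of the data".
- The PK analysis plan, Section 5, gives the planned size: "Planned enrollment is a minimum of 5 subjects aged 1 through 15 years and a minimum of 2 subjects of 4 to <12 months".

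**The concern.** Percent change divides by the baseline value, so it needs a scale on which zero means none of the quantity. Urine volume, stool count, diaper weight and ostomy output all have such a zero. A stool form category does not: its number is a label that gives order and nothing more. Renumbering the categories leaves every child's stools unchanged but alters every non-zero percent change.

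At stake is one reported row in a safety table. As the text stands, a programmer would produce percent changes in stool form next to percent changes in volume and count. A reader would have no reason to suspect that one of them depends on the coding.

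**Working it through.** **Inputs.** The SAP states no figure on this point, so there is none to reproduce. Section 13.9 gives no formula for percent change, so I use the form given in Section 11.1 for PN/IV volume:

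percent change = 100 × (visit value - baseline value) / baseline value.

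The SAP does not give the range of the stool form score. I assume integer categories 1 to 7 and compare with the same seven categories numbered 0 to 6, which is the score minus 1.

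**Algebra.** If a constant k is added to every category number, the absolute change is (v + k) - (b + k) = v - b, which does not move. The percent change becomes 100 × (v - b) / (b + k), which differs from 100 × (v - b) / b whenever v ≠ b and k ≠ 0. Averaging two daily scores does not alter this, because the average shifts by the same k.

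**Individual moves.**

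| Move (1-7 numbering) | Absolute change, either numbering | Percent change, 1-7 | Percent change, 0-6 |
|---|---|---|---|
| 2 to 4 | +2 | 100 × 2/2 = +100% | 100 × 2/1 = +200% |
| 6 to 4 | -2 | 100 × (-2)/6 = -33.3% | 100 × (-2)/5 = -40% |
| 7 to 6 | -1 | 100 × (-1)/7 = -14.3% | 100 × (-1)/6 = -16.7% |
| 2 to 1 | -1 | 100 × (-1)/2 = -50% | 100 × (-1)/1 = -100% |

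Under 0-6 numbering, a child whose baseline is the lowest category has a zero denominator and no percent change at all.

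**Group mean.** Take two subjects, the planned minimum for infants, one moving 2 to 4 and one moving 6 to 4. The mean percent change is (100 - 33.3)/2 = +33.3% under 1-7 numbering and (200 - 40)/2 = +80% under 0-6. The mean absolute change is (2 - 2)/2 = 0 under both.

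**Contrast with a measure that has a true zero.** Urine output going from 20 to 40 mL/kg/day is 100 × 20/20 = +100%. In litres it is 100 × 0.020/0.020 = +100% again. A change of unit cancels; a shift of origin does not. This is why percent change is well defined for the other measures in Section 13.9 and not for stool form.

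**The case against.** **The text may not intend it.** Section 2.2.2 speaks of fecal output by volume or count only, and the table shells are in a separate file (Section 16.1) that may already omit the row. But Section 13.9 itself counts stool form among the fecal output measures, and nothing in the SAP removes it from the percent-change instruction. The instruction therefore covers it as written.

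**Section 6.1 chooses to treat discrete-scale variables as continuous.** That choice is open to the sponsor and accommodates means and absolute differences, both of which assume equal spacing. It does not create a zero point, which percent change also needs.

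**The coding will be fixed in practice.** If the score is always recorded 1 to 7, the percent change is at least reproducible. That is fair, but reproducibility does not give the figure a meaning.

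**The consequence is small.** This stands. The same table shows absolute change, with median, minimum and maximum beside the mean. Section 7.4 sends all collected data to the listings, and at the planned minimum numbers individual scores can be read directly.

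**A stronger reading is tempting.** A reader might infer that the percent-change row reverses the true direction of effect and makes the summary uninterpretable. For example, three children moving 7 to 6, 7 to 6 and 2 to 3 have a mean change of (-1 - 1 + 1)/3 = -0.33 but a mean percent change of (-14.3 - 14.3 + 50)/3 = +7.1%. The documents do not support resting the point on this:

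- The same numbers read as stools per day give the same reversal, so it is a property of averaging percent changes over unequal baselines and not specific to an ordinal score.
- The median percent change in the example is -14.3%, in line with the mean change.
- A mean of category codes is not a true benchmark, because it also assumes equal spacing.
- No baseline scores are given, so nothing shows that such a mix of children is to be expected.

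**Conclusion.** The point holds, as a minor one. Section 13.9 prescribes percent change for an ordinal score whose percent change depends on arbitrary numbering: +100% or +200% for one move, and -33.3% or -40% for another, with the absolute change unaffected. The size of these figures rests on the assumed 1-7 coding and on the percent-change form borrowed from Section 11.1. The dependence on numbering rests only on the lack of a true zero.

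No endpoint, analysis population or decision uses this row, and the study makes no inferential claims. The other summaries of stool form remain readable, so the finding extends to the percent-change row and no further.

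**What to change.** In Section 13.9, state that percent change from baseline is presented for urine output, number of stools per day, stool/mixed stool diaper weight and ostomy output only. For the stool form score, present the observed score and the absolute change from baseline, and add the number of subjects whose score fell, was unchanged or rose. Stating the score range used in the diary would also help.

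The cost is a sentence or two in the SAP and, if the shells follow the current text, one row out and one set of counts in. Data collection and the other three fecal measures are unaffected, and no interpretable information is lost. The counts of fell, unchanged and rose depend only on the order of the categories and are easy to read with groups this small.

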13.10. PRIOR AND CONCOMITANT MEDICATIONS

Prior and concomitant medications will be coded to indication-specific preferred name using the World Health Organization Drug Dictionary. Investigator verbatim as well as coded terms will be included in the listings.

Prior medications are defined as any medication discontinued prior to the administration of study treatment. Concomitant medications are defined as any medication taken during the course of the study including medications with onset dates on or after the first dose of study medication, medications with onset dates prior to first dose of study medication without a stop date, or medications with a stop date after first dose of study medication.

Partial date imputation for medications is described in Section 6.3.

Prior and concomitant medication use will be summarized by preferred name using the number and percentage of subjects. Medications will be sorted alphabetically by preferred name. Subjects with multiple occurrences of a medication in preferred name will only be counted once within each preferred name.

A listing of all medications, both prior and concomitant, will be presented. The listing will be sorted by subject identifier and will include reported name, dose, route of administration,

T:\Shire\Teduglutide\XXA39799\Biostatistics\Documentation\SAP\SHP633-302 SAP Final

1.0_17Apr2019.docx

Author: Version Number: Final 1.0 Version Date: 17Apr2019

Template No: CS_TP_BS016 Revision 4 Reference: CS_WI_BS005

Effective Date: 01Apr2016

Document:

dosing frequency, start date, end date, indication, and period of medication (prior or concomitant).

14. CHANGES IN THE STATISTICAL METHODOLOGY PRESENTED IN THE PROTOCOL

There is no change of analysis from protocol.

15. GENERAL PROGRAMMING INFORMATION

15.1. GENERAL

All programmed table, figure and listing outputs, unless specified otherwise, will be generated using the SAS version 9.4 or later. The programmed outputs will be similar to the format/appearance of the table and listing shells. However, space/formatting limitations may dictate changes in the programmed output. The footnotes specified in the table and listing shells may be changed as necessary for clarifying table entries or the explanation of algorithms or methods used for producing the entries. Significant changes in footnotes will be discussed prior to their implementation.

15.2. FORMAT OF TABLES/LISTINGS

Tables will present subject cohorts, including all subjects and subset of subjects who began treatment after protocol amendment 3.0, in the following order: "Children (1 - 15 years) After Amendment 3", "Total Children (1 - 15 years)", "Infants (4 - <12 months)", unless otherwise specified. Note that all subjects in the infant cohort will be enrolled after protocol amendment 3.0 and thus the subset of subjects who began treatment after protocol amendment 3.0 will not be presented for the infant cohort. The following footnote will be presented in all tables/listings: "Infants are of 4 - <12 months corrected gestational age".

All output should have a 1-line footer with the SAS program name, including the path, and the date and time the output was produced at the lower left margin of the footer.

Tables and listings should be internally paginated in relation to the total length for that table or listing (i.e., Page n of N, where n is the page number within the table or listing and N is the total number of pages for that table or listing).

The table, figure and listing numbering will be based on the International Conference on Harmonization (ICH) guidelines.

A number should identify each table/listing, and the table designation (e.g., Table 1) should be centered above the title. A decimal system (e.g., x, x.y, x.y.z) should be used to identify

Document:

1.0 17Apr2019.docx

Template No: CS_TP_BS016 Revision 4

Effective Date: 01Apr2016

Author:

Copyright © IQVIA. All rights reserved.

The contents of this document are confidential and proprietary to IQVIA. Unauthorized use, disclosure or reproduction is strictly prohibited.

T:\Shire\Teduglutide\XXA39799\Biostatistics\Documentation\SAP\SHP633-302 SAP Final

Version Number: Version Date:

Final 1.0

Reference: CS WI BS005

17Apr2019

tables/listings with related contents. The title should be centered and in mixed-case characters. The title and table/listing designation should be single-spaced, but are separated from the content of the table/listing by a space and a solid underline. The study population and/or subgroup (e.g., ITT population) should be identified on the line immediately following the title.

Column headings should be in title case characters. For numeric variables, the unit should be included in the column heading when appropriate.

Footnotes should be single spaced, but separated by an underline and a space from the text of the table/listing. The notes should be aligned vertically by the left vertical border of the table/listing. Numeric references, which can be confused with data, should not be used. Rather asterisks and other non-numeric symbols should be used to refer to footnotes.

The dictionary (e.g., MedDRA, WHO-DRUG) and the dictionary version numbers should be identified in the footnotes to the tables/listings for data coded with a dictionary.

For summarizations of categorical data, an Unknown or Missing category should be added to any variable for which information is not available for all subjects. The default denominator will be all subjects in the analysis set unless otherwise specified in the SAP. For both tables and listings where there are no observations (and hence there would be no output), the table/listing should be produced with all titles and footnotes as per its shell, but with the text showing no observations in the body of the output.

Individual data listings will be sorted and presented by cohort, subject number, parameter (if applicable) and visit/collection date.

15.3. DATA FORMATS

Unless otherwise specified, means (arithmetic, geometric and 95% CI of the mean) and medians will be rounded and presented to 1 decimal place more than the raw data and standard deviations and standard errors to 2 decimal places more than the raw data. Minimum and maximum values will be presented to the same number of decimal places as the raw data. Coefficient of variation shall always be reported as a percent with 1 decimal.

Unless otherwise specified, percentages should be presented to one decimal place. Less than signs (i.e., '<') should be presented as appropriate (e.g., 0.04% should be presented as < 0.1%, not 0.0%).

Standard deviations will be calculated when the number of subjects is 2 or more.

Document: T:\Shire\Teduglutide\XXA39799\Biostatistics\Documentation\SAP\SHP633-302 SAP Final

Template No: CS_TP_BS016 Revision 4

Effective Date: 01Apr2016

Author:

Reference: CS WI BS005

Version Number:

Version Date:

Reference. CS_WI_BS005

Final 1.0

17Apr2019

16. Table, Figure and Data Listing Shells

16.1. TABLE SHELLS

See separate file.

16.2. FIGURE SHELLS

See separate file.

16.3. DATA LISTING SHELLS

See separate file.

APPENDIX 1. MARKEDLY ABNORMAL LABORATORY CRITERIA

Lab Parameter	Unit	`	- <12 months estational age)	Children (1 - 15 years)		
		Lower Limit Criteria	Upper Limit Criteria	Lower Limit Criteria	Upper Limit Criteria	
Chemistry						
Albumin	g/L	<20	>68	<20	>68	
Alkaline Phosphatase	U/L		>5 x ULN		>5 x ULN	
Alanine Aminotransferas e (ALT)	U/L		>8 x ULN		>8 x ULN	
Aspartate Aminotransferas e (AST)	U/L		>8 x ULN		>8 x ULN	
Amylase	U/L		>3 x ULN		>3 x ULN	
Lipase	U/L		>3 x ULN		>3 x ULN	
Bilirubin Total	umol/L		>5 x ULN		>3 x ULN	
Direct Bilirubin	umol/L		>68.4147		>34.208	
Blood Urea Nitrogen	mmol/L		>12.495		>12.495	
Calcium	mmol/L	<1.5	>3	<1.5	>3	
Creatinine	umol/L)	>132.6		>132.6 if age < 10 y; >150.28 if age 10- <13 y; >176.8 if age 13-<16 y; >221 if age 16+	
C Reactive Protein	mg/L		>=100		>=100	
Glucose	mmol/L	<2.22	>13.875	<2.22	>13.875	
Magnesium	mmol/L	<0.4114	>1.2342	<0.4114	>1.2342	
Phosphorus	mmol/L	<0.644	>2.254	<0.644	>2.254	

Document: T:\Shire\Teduglutide\XXA39799\Biostatistics\Documentation\SAP\SHP633-302_SAP_Final

1.0_17Apr2019.docx Author:

Template No: CS TP BS016 Revision 4

Effective Date: 01Apr2016

Version Date: 17Apr2019

Reference: CS_WI_BS005

Final 1.0

Version Number:

Copyright © IQVIA. All rights reserved.

Potassium	mmol/L	<2.5	>6.5	<2.5	>6.5
Sodium	mmol/L	<120	>160	<120	>160
Triglycerides	mmol/L		>5.65		>5.65
Hematology					
Hemoglobin	g/L	<70	>200	<70	>200
Hematocrit	fraction of 1	<0.21	>0.60	<0.21	>0.60
Platelets	10^9/L	<75	>700	<75	>700
Leukocytes	10^9/L	<2	>30	<2	>30
Neutrophils, absolute	10^9/L	<0.5		<0.5	

1.0_17Apr2019.docx

Template No: CS_TP_BS016 Revision 4

Effective Date: 01Apr2016

Author:

Copyright © IQVIA. All rights reserved.

The contents of this document are confidential and proprietary to IQVIA. Unauthorized use, disclosure or reproduction is strictly prohibited.

Document: T:\Shire\Teduglutide\XXA39799\Biostatistics\Documentation\SAP\SHP633-302 SAP Final

Version Number: Version Date:

Final 1.0 17Apr2019

Reference: CS_WI_BS005

APPENDIX 2. L, M and S Values of Height, Body Weight, BMI and Head Circumference for Age for Japanese

Table 1 L, M and S Values of Height for Age for Japanese Children

Age (yr) -		Male			Female	
Age (y1)	L	\mathbf{M}	S	L	\mathbf{M}	S
0	2.300	49.0	0.0417	1.200	48.5	0.0390
0.25	2.212	61.5	0.0378	1.159	60.1	0.0361
0.5	2.124	67.7	0.0351	1.117	66.2	0.0341
0.75	2.036	71.6	0.0335	1.076	70.2	0.0327
1	1.948	74.8	0.0328	1.034	73.5	0.0318
1.25	1.861	77.8	0.0328	0.993	76.6	0.0316
1.5	1.773	80.7	0.0332	0.952	79.5	0.0317
1.75	1.685	83.4	0.0340	0.910	82.2	0.0321
2	1.597	85.8	0.0348	0.869	84.6	0.0328
2.5	1.421	89.7	0.0364	0.786	88.4	0.0344
3	1.245	93.5	0.0378	0.703	91.8	0.0361
3.5	1.069	97.1	0.0386	0.620	95.4	0.0376
4	0.894	100.4	0.0392	0.538	99.4	0.0389
4.5	0.718	103.6	0.0397	0.455	103.2	0.0399
5	0.542	106.8	0.0403	0.372	106.7	0.0406
5.5	0.366	110.1	0.0410	0.289	109.7	0.0411
6	0.190	113.3	0.0417	0.206	112.7	0.0414
6.5	0.015	116.4	0.0423	0.124	115.5	0.0416
7	-0.161	119.5	0.0426	0.041	118.3	0.0418
7.5	-0.337	122.4	0.0426	-0.042	121.2	0.0421
8	-0.513	125.1	0.0424	-0.114	124.1	0.0428
8.5	-0.689	127.8	0.0421	-0.036	127.2	0.0438
9	-0.864	130.4	0.0420	0.213	130.4	0.0451
9.5	-1.040	133.1	0.0424	0.599	133.8	0.0466
10	-1.216	135.9	0.0435	1.055	137.2	0.0477
10.5	-1.392	138.8	0.0453	1.506	140.6	0.0481
11	-1.401	142.0	0.0476	1.879	144.0	0.0472
11.5	-0.965	145.4	0.0500	2.118	147.2	0.0447
12	-0.275	149.0	0.0519	2.190	150.0	0.0410
12.5	0.428	153.1	0.0526	2.090	152.1	0.0367
13	0.931	157.0	0.0517	1.843	153.8	0.0342
13.5	1.090	160.5	0.0491	1.498	155.1	0.0324
14	0.865	163.4	0.0453	1.124	155.9	0.0314
14.5	0.323	165.6	0.0414	0.801	156.6	0.0310
15	-0.370	167.3	0.0382	0.602	157.0	0.0310
15.5	-0.982	168.6	0.0358	0.579	157.3	0.0310
16	-1.267	169.5	0.0344	0.742	157.5	0.0310
16.5	-1.031	170.1	0.0340	1.032	157.7	0.0310
17	-0.516	170.5	0.0340	1.295	157.8	0.0310
17.5	0.000	170.8	0.0340	1.250	157.8	0.0310

Document: T:\Shire\Teduglutide\XXA39799\Biostatistics\Documentation\SAP\SHP633-302 SAP Final

1.0_17Apr2019.docx Author:

Template No: CS TP BS016 Revision 4

Effective Date: 01Apr2016

Version Number: Final 1.0 Version Date: 17Apr2019

Reference: CS_WI_BS005

IMS Health & Quintiles are now

Table 2 L, M and S Values of Weight for Age for Japanese Children

A === (===) =		Male				Female	
Age (yr)	L	M	S		L	M	S
0	0.774	3.00	0.149		0.754	2.95	0.146
0.25	0.490	6.31	0.131		0.375	5.86	0.126
0.5	0.262	7.93	0.119		0.083	7.32	0.113
0.75	0.082	8.80	0.110		-0.139	8.14	0.106
1	-0.062	9.38	0.105		-0.303	8.72	0.103
1.25	-0.177	9.91	0.102		-0.422	9.26	0.102
1.5	-0.269	10.4	0.101		-0.506	9.82	0.102
1.75	-0.344	11.0	0.102		-0.563	10.4	0.104
2	-0.408	11.5	0.103		-0.602	11.0	0.105
2.5	-0.513	12.5	0.108		-0.646	12.1	0.110
3	-0.607	13.5	0.113		-0.677	13.1	0.114
3.5	-0.703	14.5	0.119		-0.718	14.0	0.118
4	-0.804	15.5	0.123		-0.778	15.1	0.122
4.5	-0.913	16.5	0.127		-0.861	16.1	0.127
5	-1.026	17.5	0.131		-0.960	17.1	0.131
5.5	-1.136	18.5	0.134		-1.068	18.2	0.137
6	-1.236	19.6	0.138		-1.171	19.4	0.142
6.5	-1.321	20.9	0.142		-1.259	20.6	0.148
7	-1.384	22.2	0.146		-1.319	21.9	0.154
7.5	-1.420	23.5	0.152		-1.344	23.2	0.159
8	-1.429	25.0	0.159		-1.328	24.5	0.164
8.5	-1.407	26.4	0.166		-1.269	25.9	0.169
9	-1.358	28.0	0.174		-1.169	27.4	0.174
9.5	-1.284	29.6	0.182		-1.037	29.2	0.180
10	-1.191	31.4	0.189		-0.884	31.2	0.185
10.5	-1.084	33.4	0.195	1	-0.722	33.6	0.190
11	-0.971	35.6	0.200) i	-0.572	36.3	0.194
11.5	-0.862	38.1	0.204		-0.448	39.0	0.195
12	-0.764	40.7	0.206		-0.368	41.5	0.194
12.5	-0.686	43.6	0.205		-0.346	43.8	0.187
13	-0.636	46.3	0.201		-0.389	45.8	0.176
13.5	-0.619	49.0	0.196		-0.496	47.5	0.164
14	-0.642	51.6	0.187		-0.653	48.8	0.154
14.5	-0.705	54.0	0.178		-0.830	49.8	0.147
15	-0.809	55.9	0.169		-0.976	50.6	0.142
15.5	-0.952	57.5	0.161		-1.012	51.2	0.139
16	-1.127	58.8	0.155		-1.072	51.6	0.138
16.5	-1.325	59.7	0.151		-1.132	51.9	0.137
17	-1.534	60.4	0.147		-1.192	52.1	0.135
17.5	-1.739	60.9	0.141		-1.252	52.3	0.134

Document: T:\Shire\Teduglutide\XXA39799\Biostatistics\Documentation\SAP\SHP633-302_SAP_Final

1.0_17Apr2019.docx Author:

Template No: CS TP BS016 Revision 4

Effective Date: 01Apr2016

Version Date: 17Apr2019

Version Number:

Reference: CS_WI_BS005

Final 1.0

Table 3 L, M and S Values of BMI for Age for Japanese Children (Male)

Months of age	Smoothed L	Smoothed S	Smoothed M
2.5			0.032048517 x ³ + -0.493433273 x ² + 2.551397766 x + 12.62254537
9.5	1.4345E-06 x ³ -0.000119864 x ²		0.007972878 x ³ + -0.201998877 x ² + 1.54342034 x + 13.697217
9.5 +	-0.037620259 x 0.624077322	-7.58553E-08 x ³ + 2.1302E-05 x ² + -0.001094812 x + 0.090651064	-7.67459E-05 x ³ + 0.007173901 x ² + -0.251765964 x + 18.77518828
26.75			-3.88384E-06 X ³
78			+ 0.001076046 x ² -0.081944537 x + 17.20118685
90 + + +	-3.06037E-06 x ³ 0.001387949 x ² -0.190798754 x 5.531514491	0,	
150	9.04656E-07 x ³ -0.00066203 x ² 0.156555714 x -13.82908985	1.99415E-08 x ³ + -1.37006E-05 x ² + 0.002877807 x + -0.053198893	-3.94748E-06 x ³ + 0.001761925 x ² + -0.203856428 x + 22.66402577
210└			

Document: T:\Shire\Teduglutide\XXA39799\Biostatistics\Documentation\SAP\SHP633-302_SAP_Final

1.0_17Apr2019.docx Author:

Version Number: Final 1.0 Version Date: 17Apr2019

Reference: CS_WI_BS005

Template No: CS_TP_BS016 Revision 4

Effective Date: 01Apr2016

Copyright © IQVIA. All rights reserved.

Reference: CS_WI_BS005

Table 4 L, M and S Values of BMI for Age for Japanese Children (Female)

Months of age	Smoothed L	Smoothed S	Smoothed M
2.5			0.019399718 x ³ + -0.359429206 x ² + 2.139236779 x + 12.56896799
9.5 +	3.47613E-07 x ³ -2.38575E-05 x ² -0.037631412 x		+ -0.194108219 x ² + 1.537772117 x + 13.22824693
+	0.795846301	-1.0218E-07 x ³ + 2.31971E-05 x ² + -0.000923983 x + 0.08896935	-0.000168505 x ³ + 0.013702125 x ² + -0.385286062 x + 19.15626964
26.75			-4.80005E-07 x ³
69			+ 0.000350143 x ² + -0.031651293 X + 16.03450105
90 +	-5.83768E-06 x ³ 0.002194825 x ² -0.255465003 x		
+	7.295142629	2.10831E-08 x ³	-3.03967E-06 x ³ + 0.001541344 x ² + -0.183867689 x + 21.95124139
150	5.41432E-06 x ³ -0.002965041 x ² 0.532984646 x -32.85082504	+ -1.43497E-05 x ² + 0.002839146 x + -0.035441889	-2.5069E-06 x ³ + 0.000642483 x ² + 0.049828797 x + 5.323050314
210			

Document: T:\Shire\Teduglutide\XXA39799\Biostatistics\Documentation\SAP\SHP633-302_SAP_Final

1.0_17Apr2019.docx

Author: Version Number: Final 1.0 Version Date: 17Apr2019

Template No: CS TP BS016 Revision 4

Effective Date: 01Apr2016

Copyright © IQVIA. All rights reserved.

Reference: CS_WI_BS005

Table 5 L, M and S Values of Head Circumference for Age for Japanese Population

	Boys			Girls		
	LMS			LMS		
Age	L	М	S	L	М	S
Birth	3.57516	33.5340	0.041033	3.16302	33.0616	0.039349
30 days	3.51357	36.6508	0.038015	3.31746	35.8649	0.036895
1.5 months	3.47738	37.9537	0.036657	3.38432	37.0473	0.035782
2.5 months	3.39959	39.9479	0.034410	3.48864	38.8785	0.033925
3.5 months	3.31270	41.3592	0.032639	3.56084	40.2025	0.032438
4.5 months	3.21754	42.3408	0.031291	3.60300	41.1507	0.031282
5.5 months	3.11495	43.0462	0.030314	3.61724	41.8547	0.030417
6.5 months	3.00576	43.6255	0.029657	3.60563	42.4433	0.029803
7.5 months	2.89081	44.1563	0.029267	3.57027	42.9833	0.029401
8.5 months	2.77094	44.6439	0.029092	3.51326	43.4792	0.029171
9.5 months	2.64698	45.0903	0.029081	3.43670	43.9330	0.029074
10.5 months	2.51976	45.4977	0.029181	3.34267	44.3466	0.029069
11.5 months	2.39013	45.8680	0.029340	3.23327	44.7219	0.029118
12.5 months	2.25893	46.2032	0.029508	3.11059	45.0609	0.029182
13.5 months	2.12698	46.5059	0.029658	2.97674	45.3658	0.029240
14.5 months	1.99512	46.7783	0.029791	2.83380	45.6395	0.029293
15.5 months	1.86419	47.0232	0.029906	2.68386	45.8847	0.029340
16.5 months	1.73503	47.2431	0.030005	2.52903	46.1042	0.029381
17.5 months	1.60847	47.4406	0.030088	2.37140	46.3008	0.029418
18.5 months	1.48535	47.6181	0.030156	2.21305	46.4772	0.029448
19.5 months	1.36650	47.7783	0.030210	2.05609	46.6363	0.029474
20.5 months	1.25277	47.9238	0.030249	1.90261	46.7807	0.029496
21.5 months	1.14498	48.0570	0.030276	1.75470	46.9134	0.029512
22.5 months	1.04397	48.1806	0.030290	1.61446	47.0370	0.029524
23.5 months	0.95058	48.2970	0.030292	1.48399	47.1543	0.029531
27 months	0.69015	48.6746	0.030216	1.12237	47.5434	0.029525
33 months	0.45065	49.2382	0.029846	0.80613	48.1547	0.029414
39 months	0.39445	49.7113	0.029298	0.76467	48.7035	0.029206
45 months	0.43079	50.1119	0.028712	0.87148	49.1982	0.028934
51 months	0.46891	50.4577	0.028230	1.00006	49.6471	0.028633
57 months	0.41804	50.7642	0.027995	1.02390	50.0499	0.028337
63 months	0.18741	51.0444	0.028148	0.81650	50.3975	0.028081
69 months	-0.31374	51.3113	0.028831	0.25137	50.6807	0.027898
75 months	-1.17618	51.5780	0.030185	-0.79801	50.8899	0.027824

Document: T:\Shire\Teduglutide\XXA39799\Biostatistics\Documentation\SAP\SHP633-302_SAP_Final

1.0_17Apr2019.docx

Author: Version Number: Final 1.0 Version Date: 17Apr2019

Template No: CS TP BS016 Revision 4

Effective Date: 01Apr2016

Copyright © IQVIA. All rights reserved.

